6.5.3. Completer Populations

Week 12 and Week 48 completers will include subjects from the Safety Population and will be analyzed for effectiveness endpoints and are defined below.

- A Week 12 completer is defined as a subject who completes dosing through the Week 12 visit.
- A Week 48 completer is defined as a subject who completes dosing through the Week 48 visit.

These definitions ignore missed doses and treatment interruptions due to AEs.

6.5.4. Safety Population

The safety population will include all subjects who received at least 1 dose of berotralstat. This population will be used for all analyses of accountability, demographics, berotralstat drug dosing, effectiveness, compliance, and safety.

6.5.5. Pharmacokinetic Population

The PK population will include subjects in the safety population who had at least 1 evaluable and quantifiable post-dose PK sample obtained. The PK population will be the primary population for noncompartmental and population PK analyses.

6.6. Baseline Definition

For a given subject and assessment, the baseline result generally will be the latest non-missing result prior to administration of the first dose of berotralstat. The baseline ECG values will be the average of the 3 triplicate readings obtained pre-dose on Day 1. For many effectiveness endpoints, the baseline value will be based on events during the SOC period.

6.7. Derived and Transformed Data

6.7.1. Study Day

Day 1 is defined as the date of the first dose of berotralstat. If the date of interest occurs on or after the Day 1, then study day will be calculated as (date of interest – date of Day 1) + 1. If the date of interest occurs prior to the date of first dose of berotralstat (eg, during the SOC period), then study day will be calculated as (date of interest – date of first dose). There is no Day 0.

6.7.2. Change from Baseline

Change from baseline is calculated as (post-baseline result – baseline result). If either the baseline or the post-baseline result is missing, the change from baseline is set to missing as well. For laboratory values, if the baseline laboratory value is missing but a screening laboratory value exists, then the screening laboratory value may be used as the baseline value.

6.7.3. Percent Change from Baseline

Percent change from baseline is calculated as $(100 \times \text{change from baseline} / \text{baseline result})$. If either the baseline or the post-baseline result is missing, the percentage change from baseline is set to missing as well.

6.7.4. Treatment-Emergent Adverse Events

TEAEs are defined as AEs that occurred on or after first dose of study treatment through 30 days post-discontinuation of study treatment. Additionally, it is assumed that an AE which was reported to have started on Day 1 without an associated onset time may have occurred after the initiation of berotralstat. Hence, AEs occurring on Day 1 with no associated onset time will be assumed to be treatment emergent.

6.7.5. Prior and Concomitant Medications

Any medication taken within 30 days of screening and ended before study enrollment is considered a prior medication.

Any medication that is ongoing, started, or ended after enrollment is considered concomitant. It is assumed that a medication that was reported to have ended on the date of study enrollment without an associated end time may have been stopped after enrollment. Hence, medications occurring on the date of study enrollment with no associated end time will be assumed to be concomitant.

6.7.6. Treatment-Emergent Laboratory Toxicity

In general, the treatment-emergent laboratory toxicities will be graded according to the Division of Acquired Immunodeficiency Syndrome (DAIDS) Table for Grading Adverse Events for Adults and Pediatrics (Corrected Version 2.1, July 2017). Any graded clinical laboratory abnormality that occurs following the initiation of berotralstat and represents at least 1-grade increase (according to the DAIDS) from the baseline assessment is defined as treatment-emergent. However, for creatinine, the following modification will be used to target meaningful changes in creatinine in pediatric subjects with low baseline creatinine values:

- Grade 1 mild: 1.1 to 1.3 x upper limit of normal (ULN) OR increase ≥ 0.2 mg/dL from participant's baseline
- Grade 2 moderate: > 1.3 to 1.8 x ULN OR increase (≥ 1.3 x baseline AND increase ≥ 0.3 mg/dL from baseline)
- Grade 3 severe: > 1.8 to 3.5 x ULN OR (increase ≥ 1.5 x baseline AND increase ≥ 0.5 mg/dL from baseline)
- Grade 4 potentially life threatening: > 3.5 x ULN OR (increase ≥ 2 x baseline AND increase ≥ 0.7 mg/dL from baseline.)

In addition, since triglyceride values may vary depending on if the sample was taken after fasting or not, only triglyceride samples taken after fasting will be graded. Values for all other samples will have a missing grade. Non-fasting and fasting cholesterol values will be graded according to the DAIDS criteria for fasting cholesterol.

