9.3.1. Baseline Visit (Day 1)

Subjects will return to the clinic 12 weeks \pm 4 days after the date of enrollment (Section 9.2.1) for the Day 1 (baseline) visit. If extenuating circumstances would result in the baseline visit being delayed, the site must get prior approval from the medical monitor for the visit to occur outside of the defined visit window and for the subject to continue in the study. Prior to the Day 1 visit, subjects must discontinue prophylaxis for HAE as well as other specific medications.

At the baseline visit, the site will review prohibited medications (Section 8.7), subject diary entries, and discuss any AEs that occurred during the SOC treatment period. If any activities were not completed satisfactorily (eg, diary entries were incomplete or the P/C could not be contacted to assess AEs at the prescribed intervals) or the use of prohibited medications is discovered, the subject may be discontinued from the study and not enrolled into Part 1 at the sole discretion of the investigator. After final eligibility for entry into Part 1 is confirmed, subjects will receive their first dose of berotralstat in the clinic and those taking berotralstat granules for oral administration will complete the palatability/acceptability hedonic scale assessment as appropriate for the subject's age. Reference Section 8.3 for berotralstat dosing procedures. The dose of berotralstat will be determined based on the subject's weight at Day 1 and will not be adjusted during Part 1 due to weight changes. If required for medical management, any changes in berotralstat dose during Part 1 should be discussed with the BioCryst medical monitor prior to implementation. Details can be found in Section 8.4.

9.3.2. Weeks 2, 6, 9, and 12

All subjects will return to the clinic for visits during Weeks 2, 6, and 12 following baseline and the site will contact the P/C (tele-contact) during Week 9.

At the Week 2 visit, a series of blood samples will be collected for PK analysis (Section 10.9). To ensure the trough sample provides accurate PK information, the Week 2 visit should be scheduled as close as possible to the regularly scheduled time of dosing for the subject. The dose of berotralstat should be given in the clinic with food (a snack or light meal should be provided). A blood sample for PK analysis will be collected before dosing and at the times post dosing as shown in the Schedule of Assessments.

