
 • Albumin • Alkaline phosphatase (ALP) • Alanine aminotransferase (ALT) • Aspartate aminotransferase (AST) • Bilirubin (total and direct) • Blood glucose • Blood urea nitrogen (BUN) • Electrolytes (calcium, sodium, potassium, chloride, bicarbonate [CO₂], phosphorus) • Lipid panel (total cholesterol, triglycerides) • Creatine kinase • Creatinine and calculated creatine clearance (CL_{CR}) • Gamma-glutamyl transferase (GGT) • Lactate dehydrogenase (LDH) • Total serum protein • Uric acid • If amylase is > 2 × upper limit of normal (ULN), reflex to lipase 	
 • Prothrombin time (PT) and international normalized ratio (INR) • Activated partial thromboplastin time (aPTT)
	Pregnancy Test
	Only for girls who have begun to menstruate: Serum (screening) and urine (other specified visits) beta-human chorionic gonadotropin (βHCG) for girls of childbearing potential only ^a
	Hematology
Urinalysis 
 • Specific gravity • Blood • Bilirubin • Glucose • Leukocytes • Ketones • Nitrites • pH • Protein • Urobilinogen • Microalbumin to creatinine ratio • Reflex microscopy if dipstick is abnormal 	
 • Hemoglobin • Hematocrit • Erythrocytes • Mean corpuscular hemoglobin (MCH) • Mean corpuscular hemoglobin concentration (MCHC) • Mean corpuscular volume (MCV) • White blood cell count, with differential (lymphocytes, monocytes, neutrophils, eosinophils, and basophils) • Platelets
	Additional Tests
	
 • C1 esterase inhibitor (C1-INH) level and function^b • C4^b • SERPING-1 analysis^b

^a A serum pregnancy test should immediately be drawn and sent for analysis for any positive urine pregnancy test.

^b Only if required to confirm HAE diagnosis.

CL_{CR} will be calculated using the Modified Schwartz formula and actual body weight as shown in the laboratory manual.

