6.4. Data Presentation Conventions

Continuous data will be summarized using the number of subjects with available data, mean, standard deviation (SD) or standard error of the mean (SEM), median, minimum, and maximum. Categorical data will be summarized using counts/frequencies and percentages. Percentages will be calculated using the total number of subjects per cohort unless otherwise specified.

Means and medians will be formatted to 1 more decimal place than the measured value, SDs and SEMs to 2 more decimal places, and minimum and maximum values to the same number of decimal places. For categorical variables, the number and percentage of responses will be presented in the form XX (XX.X%) where the percentage is in the parentheses, except that 100% will be presented to 3 digits with no decimal. Adverse event data will be presented in the form XX (XX.X%) [XXX] where the number of subjects with at least 1 event (incidence) is the first number and the number of occurrences of an event is in “[]”. Dates will be formatted as DDMMYYYY and times will be formatted in 24-hour time as HH:MM. Partial dates will be handled as described in Section 8.5.

Berotrastat concentration data will be listed and summarized as part of the statistical analysis for this study and included in the Clinical Study Report. Noncompartmental PK parameters will be calculated as described in Section 10.1.2 and included in the Clinical Study Report. PK parameters from population PK modeling will be calculated and summarized as described in the Population PK Analysis Plan and included in the Population PK report.

Wherever possible, data will be decimal aligned.

A table of contents at the end of this SAP provides the expected titles and numbers of the tables, listings, and figures of the final report. Changes to titles or numbering in the final report will not necessitate a revision to the SAP, nor will they be considered deviations from planned analyses. Additional data listings supporting the tables will not be considered a deviation from planned analyses.

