11.3.1. Analysis of Abnormal Laboratory Values

Laboratory abnormalities will be graded according to the DAIDS (also see Section 6.7.6). Treatment-emergent graded toxicities are defined in Section 6.7.6 (including exceptions) and the number and percentage of subjects who experience treatment-emergent graded toxicities will be summarized by panel, parameter, time point, and cohort.

Laboratory toxicity shifts from baseline to worst post-baseline grade will be summarized by panel, parameter, toxicity grade, and cohort.

The following categories of abnormal hepatic laboratory values will be evaluated for any occurrence among all post baseline assessments (where “and” indicates elevations occurring at the same visit). Within each treatment group and laboratory parameter grouping, a subject may be counted once per elevation criteria using the worst-case result. That is, a subject with a worst-case alanine transaminase (ALT) elevation $>3 \times$ the ULN for a given treatment group would be counted once in the ALT $> 1.5 \times$ ULN category and once in the ALT $> 3 \times$ ULN

category, regardless of how many ALT elevations the subject had that met the $> 3 \times \text{ULN}$ and $> 1.5 \times \text{ULN}$ elevation criteria.

- ALT and/or aspartate transaminase (AST) $> 3 \times \text{ULN}$ and total bilirubin > 1.5 or $2 \times \text{ULN}$
- AST $> 1.5, 3, 5, 10,$ and $20 \times \text{ULN}$
- ALT $> 1.5, 3, 5, 10,$ and $20 \times \text{ULN}$
- Total bilirubin $> 1, 1.5,$ or $2 \times \text{ULN}$
- Alkaline phosphatase (ALP) $> 1.5 \times \text{ULN}$

Profiles of liver enzymes and bilirubin over time will be graphically displayed for subjects with any Grade 3 or 4 abnormality in these analytes. In addition, a listing of all liver function test (ALT, AST, bilirubin, ALP, gamma-glutamyl transferase) results for subjects experiencing a treatment-emergent Grade 3 or 4 liver function test will be provided.

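### Children with no gradable (fasting) triglyceride stay in the percentage denominator, so the triglyceride toxicity percentages are biased toward zero by a share the plan does not report.

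*SAP*

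**What the plan says.** - **Grading.** SAP 6.7.6: "only triglyceride samples taken after fasting will be graded. Values for all other samples will have a missing grade". The same section grades cholesterol whether or not the child fasted.
- **Treatment-emergent.** SAP 6.7.6: a graded abnormality after the start of berotralstat that "represents at least 1-grade increase (according to the DAIDS) from the baseline assessment is defined as treatment-emergent".
- **Summary.** SAP 11.3.1: "the number and percentage of subjects who experience treatment-emergent graded toxicities will be summarized", by panel, parameter, time point and cohort. Shifts from baseline to worst post-baseline grade are also tabulated. No denominator is given for either.
- **Default denominator.** SAP 6.4: "Percentages will be calculated using the total number of subjects per cohort unless otherwise specified".
- **Baseline.** SAP 6.6 takes the latest non-missing result before the first dose. SAP 6.7.2 allows a screening laboratory value to stand in when the baseline value is missing. Neither section covers a value that is present but has no grade.
- **Fasting.** Protocol Table 3 lists triglycerides in the lipid panel without a fasting condition. The schedule of assessments and Protocol 10.7 add none. Protocol 9.3.2 has the Week 2 dose given in the clinic with a snack or light meal. After Week 2, Protocol 8.3.2 has the dose taken with the largest meal of the day and not re-timed for visits.

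**The concern.** Fasting-only grading is sound in itself, because the DAIDS triglyceride row in the protocol appendix is defined for fasting values. The difficulty is what happens to the children it leaves out. They cannot enter the numerator, they remain in the denominator, and so they are read as free of toxicity.

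Elsewhere the SAP resolves missing safety information cautiously. A missing severity becomes Grade 3 and a missing relationship becomes related (SAP 8.5.8), and an untimed Day 1 event becomes treatment-emergent (SAP 6.7.4). Here a missing grade works in the opposite direction.

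At stake is the reading of one laboratory parameter in a study of about 30 children with cohort minimums of 3 or 4. From the percentage alone, a triglyceride entry of 0% could mean that no toxicity occurred or that few children could be graded.

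**Working it through.** **1. The plan's own figure.** Protocol 12.1 gives about a 96% chance of seeing at least one event with a 10% rate among 30 subjects. 1 − 0.9^30 = 0.958, so it reproduces. It presumes that all 30 children can be assessed for the event.

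**2. Effect of the denominator.** Let r be the true share of children with the toxicity and f the share who can be counted. Assume that fasting status is unrelated to toxicity and that a countable child's toxicity is captured. With all subjects in the denominator, reported % = r × f. With countable children only, the expected value is r for any f > 0. The value r = 10% below is borrowed from the sample-size statement for illustration; it is not a triglyceride estimate.

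| f | Reported %, all subjects (10% × f) | Countable children of 30 | Chance of at least 1 case, 1 − (1 − 0.10f)^30 |
|---|---|---|---|
| 0.10 | 1.0% | 3 | 26% |
| 0.25 | 2.5% | 7.5 | 53% |
| 0.50 | 5.0% | 15 | 79% |
| 0.75 | 7.5% | 22.5 | 90% |
| 1 | 10% | 30 | 96% |

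Changing the denominator corrects the percentage. It does not recover the cases lost among ungraded children.

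**3. How large f might be.** The schedule has six post-baseline chemistry panels to Week 48: Weeks 2, 6, 12, 24, 36 and 48. Let p be the chance that a sample is fasting. It is not in the documents, so a range is shown, with samples assumed independent and no dropout. Three baseline rules are possible:

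- A: an ungraded baseline counts as grade 0. f = 1 − (1 − p)^6.
- B: a graded Day 1 baseline is required. f = p × [1 − (1 − p)^6].
- C: a graded value at Day 1 or screening is required. f = [1 − (1 − p)^2] × [1 − (1 − p)^6].

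| p | A | B | C |
|---|---|---|---|
| 0.1 | 0.469 | 0.1 × 0.469 = 0.047 | 0.19 × 0.469 = 0.089 |
| 0.2 | 0.738 | 0.2 × 0.738 = 0.148 | 0.36 × 0.738 = 0.266 |
| 0.3 | 0.882 | 0.3 × 0.882 = 0.265 | 0.51 × 0.882 = 0.450 |
| 0.5 | 0.984 | 0.5 × 0.984 = 0.492 | 0.75 × 0.984 = 0.738 |

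At p = 0.2 the choice between A and B changes the countable share five-fold (0.738 / 0.148 = 5.0). Read literally, SAP 6.6 and 6.7.2 do not lead to C: a non-fasting Day 1 triglyceride is a non-missing value, so it remains the baseline and carries no grade.

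**4. Sensitivity to independence.** If each child either always or never fasts, A, B and C all give f = p, that is 10% to 50% over the same range.

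**5. Which table.** The formulas in step 3 apply to treatment-emergent toxicity. Among the listed tables that is 14.3.4.3, restricted to Grade 3 and 4, which for triglycerides means above 500 mg/dL. The shift table 14.3.4.4.1 does not use the treatment-emergent definition, so the step 3 shares do not carry over. The direction of bias is the same, because ungraded children still sit in its default denominator.

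**The case against.** A reader might infer that triglyceride toxicity will be reported close to zero by construction, whatever the drug does. The documents do not support that.

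- The fasting share is unknown. The absence of a fasting requirement is not the absence of fasting samples. Protocol 10 places dosing at the end of the visit where possible, doses up to the Week 2 visit are taken with a morning meal, and SAP 11.3.1 plans separate fasted and non-fasted triglyceride summaries, so both kinds are expected. A laboratory manual that is not among the documents may also say something about fasting.
- The lowest shares, 5% to 49%, depend on requiring a graded baseline, which the SAP does not state.
- Values are not lost from view. Non-fasting results remain in the change-from-baseline summaries, the distribution plots and the listings, and a finding judged clinically significant is recorded as an adverse event.

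All of this stands, and it limits the point to the graded tables.

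A further objection is that SAP 6.2 already has tables show how many subjects the data apply to and separate unknown or unperformed results from missing ones. The table shells, which are in a separate document, may do this for triglycerides. That might put a number of graded children on the page. It is a general format statement, however, and does not alter the SAP 6.4 denominator, so the printed percentage would still be too low.

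**Conclusion.** The point holds as a small correction to the counting rule. Fasting-only grading, no stated fasting requirement and an all-subjects denominator together bias the triglyceride toxicity percentages toward zero by the factor f.

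The size is not fixed by the documents. Under the stated assumptions (p from 0.1 to 0.5, six independent panels, toxicity unrelated to fasting), f for treatment-emergent toxicity runs from 47% to 98% when an ungraded baseline counts as grade 0, and from 5% to 49% when a graded baseline is required. A true 10% would then print as anything from about 0.5% (10% × 0.047) to about 9.8% (10% × 0.984). That width is itself part of the finding: an unstated programming decision and an unreported fasting share determine the result. If one fasting sample does not capture a transient elevation, the printed figure would be lower still.

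**What to change.** Keep fasting-only grading and amend SAP 11.3.1, with a matching line in 6.7.6:

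- For triglycerides, use as denominator the children with at least one graded post-baseline value, and print that n in Tables 14.3.4.3 and 14.3.4.4.1.
- In the shift table, show an ungraded baseline or post-baseline result as its own missing category.
- When the Day 1 triglyceride is non-fasting, take the baseline grade from a fasting screening sample if there is one. Show children who still have no baseline grade on a separate line, outside the treatment-emergent percentage, so that they are read neither as free of toxicity nor as emergent cases.

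Counting every graded abnormality as emergent when the baseline is ungraded would be a more cautious alternative. It is debatable, because it could label a pre-existing elevation as emergent, and the correction does not depend on it.

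The cost is a few sentences. No new samples are needed, provided fasting status is recorded as SAP 6.7.6 already presupposes. The downside is that percentages will rest on a visibly small n; with cohort minimums of 3 or 4 it could be 1 or 2 in a cohort.

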6.7.7. Derived Effectiveness Endpoints

6.7.7.1. Subject-Reported Attack

A subject-reported attack is any attack reported on the HAE Attack Details eCRF page. Each reported attack will count as a separate attack, even if the time periods for the attacks are overlapping.

6.7.7.2. Adjusted Attack

Subject-reported attacks reported must meet the following criteria (applied in order) for inclusion in effectiveness analyses:

- Attack must include at least 1 symptom of swelling;
- Subject response to diary question, “In retrospect, could there be an alternative explanation for your symptoms other than an HAE attack (ie, allergic reaction, viral cold etc.)?” must be “no”.
- Attack must be unique (attack began > 24 hours from the end of the prior attack);
- Any attack that begins within 24 hours from the end of a prior attack will be combined with the prior attack;

- If the entire adjusted attack is untreated, it must have a duration > 24 hours.

Using the above criteria, adjusted attacks will be determined programmatically. For adjusted attacks that span 2 or more subject-reported attacks, attack triggers, locations, symptoms, duration, and other characteristics will be based on the information from each component subject-reported attack. Additionally, the start date/time of the adjusted attack will be the start date/time from the first attack and then end date/time of the adjusted attack will be the end date/time from the last attack being collapsed programmatically.

6.7.7.3. Baseline Attack Rate

The baseline attack rate will be calculated using data from the SOC period and standardized to number of attacks per month, where 1 month is defined as a 28-day (4 week) period. It is calculated as:

$$\frac{\text{Number of HAE attacks during the SOC period Screening} * 28}{\text{Study Day 1 Date} - \text{Screening Date} + 1}$$

where the number of HAE attacks during SOC period includes any attacks starting after informed consent through the time of first dose. The screening day is the first day of the SOC period. Note that the SOC period starts upon signing the informed consent form. A similar method will be used to calculate other baseline rates (eg, baseline HAE attacks treated with rescue medication).

6.7.7.4. Attack Rate in Parts 1 and 2

The observed attack rate will be computed as the number of attacks per month, where 1 month is defined as a 28-day (4-week) period.

In general, the formula for computing an attack rate is the number of attacks meeting the attack criteria divided by the duration of the reporting period of interest.

$$\text{Attack Rate} \left(\frac{\text{attacks}}{\text{month}} \right) = \frac{\text{Number of Attacks} * 28}{\text{Duration of Treatment Period of Interest}}$$

For subjects who complete the reporting period of interest, duration of reporting period of interest is defined as the last day in the reporting period – first day in reporting period + 1. For subjects who discontinue treatment prematurely in the reporting period of interest, the duration of reporting period of interest is defined as (last day of treatment +1) – first day in reporting period + 1. For example, if a subject receives the last treatment on Day 13 of Month 3 with 2 attacks between Day 1 and Day 14, that subject will be considered to have had a rate of 4 attacks/month ($2 \times 28/14 = 4$) for Month 3. Both the reporting period and the treatment period have been adjusted to include an additional day as the subject prematurely discontinued dosing in Month 3.

Subject-Reported Attack Rate

Subject-reported attack rates will be computed through Week 12 and through Week 48 (eg, 0-12 weeks and 0-48 weeks).

Adjusted Attack Rate

Adjusted attack rates will be computed for the following reporting periods of interest and expressed in units of attacks/month where 1 month = 28 days:

- During SOC
- By month
- Through Week 12 (eg, 1-12 weeks)
- Through Week 48 (eg, 1-48 weeks)

Adjusted attack rates will be calculated during the SOC period as well as study Parts 1 and 2. For on-study adjusted attack rates by month, months will be defined in blocks of 28 days, beginning on Day 1, after the first dose of berotralstat. If an attack occurs on Day 1, and the time of both the attack and berotralstat administration are recorded, then an attack prior to berotralstat should be counted in the SOC period and an attack after berotralstat administration should be counted in Week 1 (Month 1). Should a subject prematurely discontinue treatment at the end of the monthly reporting period (ie, Day 28), any attacks that occur within 24 hours after last dose will be counted in the calculation of attack rate of the prior month and the additional 24-hour period will be included in the duration of the reporting period. For example, if a subject has 1 attack from Day 1 to 28, discontinues drug on Day 28, and has an attack on Day 29, the Month 1 (Day 1 to Day 28) attack rate will be 0.55 attacks/month ($2 \times 28/29 = 0.55$). Since HAE attack data are only to be collected during SOC, Part 1, and Part 2, an attack that numerically falls beyond Week 48 will be included with data in Week 48 (Month 12) if it occurs on or prior to the Week 48 visit (also see Table 5).

No imputation will be done for missing data.

